6.4 Outcomes

6.4.1 Quasi-experimental pre-post study

Two primary outcomes will be assessed between the pre-intervention and post- intervention period:

- ξ Proportion of children referred by a primary care healthcare provider to a higher level of care (either to a hospital or to an inpatient part of a larger primary healthcare facility) at Day 0 consultation
- ξ Proportion of children prescribed an antibiotic at Day 0 primary care consultation

These two outcomes are selected to reflect the intended impact on referral of children with severe disease (pulse oximetry and CDSA) and antimicrobial stewardship (CDSA). Severe complication outcomes are included in secondary outcomes rather than primary as, given the pre-post nature of the study, change in mortality / morbidity outcomes could be influenced by other events occurring between the baseline and post-intervention comparison phase.

Secondary outcomes:

- ξ Proportion of children with a severe complication (death or secondary hospitalisation) by Day 7
 - Secondary hospitalisation refers to any delayed hospitalisation (occurring at any point greater than 24 hours after Day 0 consultation) and any hospitalisation occurring without referral. The denominator is all enrolled children
- ξ Proportion of children admitted to hospital within 24 hours of the Day 0 primary care consultation and as a result of a referral
 - This is used as a proxy for 'appropriate referral' of children, as those with severe disease should generally be admitted to hospital. The denominator for this outcome is also all children enrolled in the study, rather than only referred children. This is because the proportion of referred children that are admitted may be high in routine care, in the context of an inappropriately low referral rate. The aim of the intervention is therefore to increase the overall referral rate of children with severe disease. Hospital admission is chosen as the proxy of severe disease rather than using primary care classification of severe disease, as there are inadequacies in the classification of severe disease in routine practice
- ξ Proportion of children who completed referral as reported at day 7 follow-up
- ξ Proportion of children cured (defined as caregiver reported recovery from illness) at Day 7 follow-up

Sub-groups for analysis of primary and secondary outcomes:

- ξ Age (under 2 months, 2 – 12 months, 13 – 59 months)
- ξ Sex
- ξ Presentation with cough / difficulty breathing

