3.1.4 Outcomes

This section provides an overview of the outcomes as listed in the protocol.

Primary outcomes

- ξ Proportion of children referred by a primary healthcare provider to a higher level of care at Day 0 consultation
- ξ Proportion of children prescribed an antibiotic at Day 0

Secondary outcomes

- ξ Proportion of children with a severe complication by Day 7
- ξ Proportion of children admitted to hospital within 24 hours of the Day 0 consultation and as a result of a referral (this is a proxy for 'appropriate referral' of children)
- ξ Proportion of children cured at Day 7 follow-up
- ξ Proportion of children who completed referral as reported at Day 7 follow-up

Other outcomes of interest – hypoxaemia (in post-intervention only)

- ξ Proportion of children with severe ($\text{SpO}_2 < 90\%$), moderate ($\text{SpO}_2 90 – 91\%$) and mild ($\text{SpO}_2 92 – 93\%$) hypoxaemia, adjusted for sites at high altitude
- ξ Proportion of children with hypoxaemia (according to differing cut-offs) with severe complication
- ξ Proportion of children with severe hypoxaemia not meeting any other clinical criteria for severe disease
- ξ Proportion of children referred with hypoxaemia who receive oxygen at hospital

Other outcomes of interest – referral and follow-up

- ξ Proportion of children with non-severe disease referred to a higher level of care on Day 0
- ξ Average length of stay (in days) of children admitted to hospital
- ξ Proportion of children attending scheduled follow-up at the same facility by Day 7
- ξ Proportion of children presenting for unscheduled follow-up to any health facility by Day 7

Other outcomes of interest – antimicrobial prescription

- ξ Proportion of children prescribed a diagnosis-appropriate antibiotic
- ξ Proportion of febrile children tested for malaria at Day 0
- ξ Proportion of malaria positive children prescribed an antimalarial
- ξ Proportion of malaria negative children prescribed an antimalarial
- ξ Proportion of untested children prescribed an antimalarial

Other factors for exploratory analyses

- ξ Additional socio-demographic characteristics, urban / rural location, distance from health facility, key household indicators such as maternal age and education
- ξ Main complaint / symptom categories (including cough / difficulty breathing, fever, diarrhoea and other) and time since onset of symptoms
- ξ Alternative hypoxaemia cut-offs
- ξ Health care provider severity classification

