6.1.1 General definitions

Day 7 assessment

Day 7 assessment refers to information reported by the caregiver after Day 0 and recorded in Day 7 form. Data collected as part of unscheduled visits are also integrated in these forms. If multiple successful follow-up assessments for the same child are recorded within the Day7 database, the most recent follow-up assessment will be used. To limit potential recall bias, assessments conducted far beyond the expected follow-up time will be dropped, i.e. 30 days from Day 0.

Death

A child will be considered deceased if, from Day 7 assessment, his/her status at the time of follow-up is “deceased”. In case of implausible death date (i.e. prior to enrolment date), death will be assumed to be within 7 days of Day0.

Hospitalisation

A child will be considered hospitalised if, from Day 7 assessment, he/she went to a hospital, was admitted overnight or if his/her status at the time of follow-up is “hospitalised”. In case of implausible hospitalisation date (i.e. prior to enrolment date), hospitalisation will be assumed to be within 7 days but after 24hrs of Day0.

Hospitalisation within 24hrs of Day0

For the purpose of primary analysis, a child will be considered admitted to hospital within 24hrs of Day0 consultation if the date of hospitalisation is the same as Day0 date or is one day after Day0 date.

Referral

A child will be considered to be referred (either to a hospital or to an inpatient part of a larger primary healthcare facility) if, at Day0, the research assistant confirms that an urgent referral advice was recorded for the child. If urgency is unknown, referral will be assumed to be urgent.

Antibiotics

Antibiotics will be defined in accordance with the WHO antibiotic point prevalence survey (PPS) methodology [4, 5, 6] and therefore only antibacterials for systemic use will be taken into account.

SpO2 values

SpO₂ should be recorded during the Day0. For the outcomes, the following measures will be taken for spurious and missing SpO₂ values:

- If SpO₂ value is not available, the child will be assumed normoxaemic
- If $70 \leq \text{SpO}_2 < 90\%$, the child will be assumed (with accuracy) to have severe hypoxaemia
- If $40 \leq \text{SpO}_2 < 70\%$, the child will be assumed (with low accuracy) to have severe hypoxaemia
- If $\text{SpO}_2 < 40\%$, the value will be considered spurious (e.g. due to incorrect dataentry) and treated as not available, i.e. the child will be assumed normoxaemic.

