6.1.2.3 Average length of stay (in days) of children admitted to hospital

Length of stay is defined as hospitalisation duration in days as reported by the caregiver at Day 7. If a child is hospitalised twice, the first hospitalisation will be used and second hospitalisations will be reported separately. The denominator will be all hospitalised children.

6.1.2.4 Proportion of children referred by a primary healthcare provider to a higher level of care at Day 0 consultation

All children who received a referral advice (as per definition above) at Day0 will be counted in the numerator. The denominator will be all children recruited.

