6.2.4 Pre-planned Sensitivity Analyses

Sensitivity analyses on the primary outcomes are planned and will be conducted:

- ξ On first encounters, which will include only the first enrolment episode of each child during the study period (as some children may attend the facility on more than one occasion). Separate presentations are identifiable from Day0 form as the caregiver is asked whether the child attended previously and within 28 days. This is the minimum number of days required for the disease episode to be considered a new one and not a repeat visit.
- ξ Looking at different referral definitions¹:
 - ο A child will be considered to be referred if, at Day0, the caregiver confirms that the child was urgently referred or the research assistant confirms that an urgent referral advice was recorded for the child. If urgency is unknown from both sources, referral will be assumed to be urgent.

¹ Urgency, as reported by the caregiver, was introduced only in the post-intervention period in Kenya. For the pre-intervention period, urgent referrals will be defined based on the registry alone, as described for the primary analysis.

- A child will be considered to be referred if, at Day0, caregiver confirms that the child was urgently referred *and* the research assistant confirms that an urgent referral advice was recorded for the child.

Additionally, a set of sensitivity analyses shall be carried out based on different definitions of pre and post-intervention periods:

- ξ Pre-intervention and post-intervention defined based on periods of the year that match in the pre and post intervention.
- ξ Pre-intervention defined as primary analysis and post-intervention from country-specific relevant dates (i.e. formal initiation after the strike in Senegal and intensive supervision in Kenya) to the end of data collection.

Sensitivity analyses on the secondary outcomes related to hospitalisation will be conducted looking at different hospitalisation appropriateness (based on different definitions of primary and secondary hospitalisations). Same day (Day0), 3 days and 7 days from Day0 will be used as cut-offs for different primary and secondary hospitalisation definitions.

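### The SAP narrows the primary referral outcome to urgent (or unknown-urgency) referrals without declaring it, and no pre-specified analysis counts all referrals

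*SAP*

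**What the plan says.** Protocol 6.4.1 gives the first primary outcome as "Proportion of children referred by a primary care healthcare provider to a higher level of care", assessed on Day 0. The SAP overview (3.1.4) repeats it: "Proportion of children referred by a primary healthcare provider to a higher level of care at Day 0 consultation". Neither sets a condition on urgency. The sample size sections (Protocol 6.6.1, SAP 3.4) assume a 3% pre-intervention rate, also without mentioning urgency.

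SAP 6.1.1 then defines referral more narrowly. A child counts if "the research assistant confirms that an urgent referral advice was recorded for the child". The rule for gaps is: "If urgency is unknown, referral will be assumed to be urgent". SAP 6.1.2.4 carries this into the primary outcome: "All children who received a referral advice (as per definition above) at Day0 will be counted in the numerator". The same definition feeds the outcomes on admission after referral (6.1.2.2), completed referral (6.1.2.5) and referral of children with non-severe disease (6.1.2.6).

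SAP 6.2.4 offers two alternative definitions. The first accepts an urgent referral from either the caregiver or the record, with the rule: "If urgency is unknown from both sources, referral will be assumed to be urgent". The second needs both sources: that the "caregiver confirms that the child was urgently referred" and that the record shows urgent advice. A footnote adds: "Urgency, as reported by the caregiver, was introduced only in the post-intervention period in Kenya". It says that pre-intervention classification there rests on the register alone.

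SAP 1.1 says that the plan follows the protocol unless it states otherwise. It states no departure for referral. SAP 6.3 expects no missing data on the primary outcomes and does not mention unknown urgency.

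**The concern.** Two things follow from setting these sections side by side.

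First, the quantity to be estimated is not the one that the protocol words. A referral recorded as non-urgent meets the protocol's description and fails the SAP's. The change sits in a list of general definitions, with no statement that it is a change and no reason given.

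Second, the counting rule makes completeness of urgency recording part of the outcome. A non-urgent referral counts if nobody noted its urgency and does not count if somebody did. In a before-after comparison without concurrent controls, a change in that completeness between periods would show up as a change in referral.

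**Working it through.** **1. Which referrals each definition counts**

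| Definition | Urgent | Non-urgent | Unknown urgency |
|---|---|---|---|
| Protocol 6.4.1, SAP 3.1.4 | yes | yes (no condition stated) | yes |
| SAP 6.1.1 and 6.1.2.4 (primary) | yes | no | yes |
| SAP 6.2.4, caregiver or record | yes, from either source | no | yes, if unknown from both |
| SAP 6.2.4, caregiver and record | yes, if both agree | no | no rule given; apparently not counted |

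No row below the first counts non-urgent referrals. In Kenya the last two rows use the register alone before the intervention and two sources after it, so they do not compare like with like there.

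**2. The plan's own sample size**

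Inputs from Protocol 6.6.1: 3% against 4.5%, power 80%, alpha 0.05, ICC 0.005, and 690 (Kenya) or 510 (Senegal) children per facility per period. Two-sided testing is taken from the two-sided intervals in SAP 4.1.

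- n = [1.960·√(2·0.0375·0.9625) + 0.842·√(0.03·0.97 + 0.045·0.955)]² / 0.015², which rounds up to 2,518 per period.
- Design effects: 1 + 689·0.005 = 4.445 and 1 + 509·0.005 = 3.545.
- Facilities: 2,518·4.445/690 = 16.22, so 17 (11,730 children). 2,518·3.545/510 = 17.50, so 18 (9,180 children).

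Both match the protocol exactly. The design is therefore sized on the unqualified 3%.

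**3. Effect of the rule for unknown urgency**

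Let r be the rate of all referrals, u the urgent share where urgency is known, and k the share with unknown urgency. Counted rate = r·[k + (1 − k)·u]. The documents give neither u nor k, so both are assumed. With r = 3% in both periods and k falling from 50% to 0%:

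| u | Counted pre | Counted post | Ratio | Ratio if k rises from 0% to 50% |
|---|---|---|---|---|
| 50% | 2.25% | 1.50% | 0.67 | 1.50 |
| 60% | 2.40% | 1.80% | 0.75 | 1.33 |
| 70% | 2.55% | 2.10% | 0.82 | 1.21 |
| 80% | 2.70% | 2.40% | 0.89 | 1.13 |
| 90% | 2.85% | 2.70% | 0.95 | 1.06 |

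A fall in k from 30% to 0% gives 0.77, 0.83, 0.89, 0.93 and 0.97 for the same values of u. At the initially planned size, a 50-point change would reach significance about 52% of the time at u = 50%, 33% at 60% and 10% at 80%.

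If all referrals truly rise from 3% to 4.5% while k falls from 50% to 0%, the counted ratio is 1.00, 1.13, 1.24, 1.33 or 1.42 for u = 50% to 90%, against a true 1.50.

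**4. Power for urgent referrals alone, with no unknowns**

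Effective sizes per period are 11,730/4.445 = 2,639 and 9,180/3.545 = 2,590. For the same 50% relative rise:

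| Urgent share (assumed) | Rates compared | Power, Kenya / Senegal |
|---|---|---|
| 100% | 3.00% and 4.50% | 0.82 / 0.81 |
| 90% | 2.70% and 4.05% | 0.78 / 0.77 |
| 70% | 2.10% and 3.15% | 0.67 / 0.66 |
| 50% | 1.50% and 2.25% | 0.52 / 0.51 |

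**The case against.** There is a good case for the urgent definition. Protocol 6.4.1 says that the outcome is meant to reflect referral of children with severe disease, and urgent advice is a reasonable measure of that. Protocol 7.3 leaves statistical detail to the SAP. The protocol does not say in terms that urgency is irrelevant, and its 3% comes from informal estimates and survey data that may or may not include non-urgent referrals. If the intervention acted only on urgent referrals, their relative rise would exceed 50% (for example 2.1% to 3.6%, a ratio of 1.71, at a 70% urgent share), and the power loss above would not arise. All of this stands. It supports the choice of definition but not leaving it undeclared.

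There are also safeguards against unknowns. Day 0 entry is compulsory (SAP 6.3), and research assistants ask the provider when the referral advice in the records is unclear (Protocol 7.1.1). Unknown urgency may be rare, although the SAP expects enough of it to write a rule. The definition that requires both sources appears to drop unknowns, so it partly tests the rule in Senegal.

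A reader might infer three stronger things, and the documents support none of them.

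- That the Kenya footnote shows a change in how the primary outcome was recorded. It concerns the caregiver's report, which enters only the sensitivity definitions. The primary definition uses the record, and nothing says that recording of urgency there changed.
- That the decision support tool makes urgency recording more complete and so pushes the result downwards. No section says that the tool alters how urgency appears in the records, and the direction is not fixed.
- That counting all referrals is immune to recording changes. It removes the dependence on urgency, but better documentation could also raise the number of referrals recorded at all.

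**Conclusion.** The undeclared narrowing stands on the text alone and needs no assumption: the protocol-worded primary outcome has no pre-specified analysis. SAP 1.1 permits unplanned analyses, but these do not replace a pre-specified primary outcome.

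The bias from the rule for unknown urgency is a possibility only. It is small if nearly all referrals are urgent or if unknowns are equally rare in both periods. It could be as large as the whole planned effect if about half of referrals are non-urgent and the unknown share moves by 50 points. The power figures rest on an assumed urgent share, an equal relative rise in urgent and non-urgent referrals, a 3% that includes both, and the initial sample size. The documents say that the size was later revised but give no new total.

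**What to change.** - Pre-specify an analysis of all recorded Day 0 referrals, whatever their urgency, with the same primary model. Report it as the protocol-worded outcome beside the urgent version.
- State in the SAP that the urgent definition departs from the protocol wording, and give the reason.
- Add a sensitivity analysis that counts unknown urgency as non-urgent.
- Tabulate urgent, non-urgent and unknown referrals by period and country.
- Note that in Kenya the two caregiver-based definitions use different sources in the two periods.

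The cost is two extra model specifications, one table and a short paragraph. It assumes that non-urgent referrals are held in the Day 0 data in both periods, as the SAP's separation of urgent from unknown implies; the data form should be checked. If the SAP can no longer be amended, SAP 1.1 allows the same analyses as labelled and justified additions.

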4.2 Intervention adherence and Protocol Deviations

While in Kenya pulse oximeter was indicated for all children, in Senegal, pulse oximeter was indicated for all young infants and for older children with cough/difficult breathing or red/yellow IMCI classification. Cough/difficulty breathing and red/yellow IMCI classification are defined two ways, based on signs and symptoms as reported by the caregiver pre-consultation or on diagnosis made by the healthcare provider during the consultation. These definitions are detailed in a separate document and both will be used, separately, to assess intervention adherence.

Adherence will be evaluated on the basis of pulse oximeter and CDSA use when indicated.

- ξ Pulse oximetry adherence will be evaluated primarily using information on SpO2 values from clinical records. Pulse oximetry will be considered used if the RA has found any SpO2 recording (value readable or unreadable). Pulse oximetry will be considered not used if the RA did not find any recorded SpO2. Adherence will be additionally evaluated based on pulse oximetry use as reported by the caregivers.

- ξ CDSA adherence will be evaluated by comparing the number of children enrolled and the number of children recorded into the CDSA database. These data will be used to explore further and in more details adherence to the CDSA, but outside the scope of this SAP and it will be detailed in a separate document.

Adherence will be reported overall and weekly by facility.

The following information will be summarised by arm to evaluate deviations to the study protocol:

- ξ Number and percentage of caregivers for which no Day 7 follow-up was attempted.

More general deviations will be recorded by the study team in a study deviation log and categorised into minor and major.

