6 ANALYSIS

Analyses will be performed and reported overall and by country.

Outcomes will be presented separately for young infants (<60 days) and older children (60 days-59 months), the malaria-related outcomes will be presented only on older children.

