6.1.5 Hypoxaemia-related outcomes – in post-intervention only

6.1.5.1 Proportion of children with severe, moderate and mild hypoxaemia, adjusted for sites at high altitude

Hypoxaemic children will be summarised disaggregated by groups based on the following SpO₂ values ranges: SpO₂ < 90%, 90% ≤ SpO₂ < 92% and 92% ≤ SpO₂ < 94%. All children recruited will be in the denominator.

All facilities in Senegal are in low altitude area and therefore no adjustment is required. Only few facilities from one district in Kenya were above 2000m but cut-off for referral was not adjusted and therefore no adjustment will be applied.

6.1.5.2 Proportion of children with hypoxaemia (according to differing cut-offs) with severe complication

Children with severe complication will be summarized disaggregated by groups based on the following SpO₂ values ranges: SpO₂ < 90%, 90% ≤ SpO₂ < 92% and 92% ≤ SpO₂ < 94%, spurious values and missing values. Each SpO₂ group will be the denominator of each proportion.

6.1.5.3 Proportion of children with severe hypoxaemia not meeting any other clinical criteria for severe disease

Children with severe hypoxaemia (according to country's specific cut-off) not meeting any other clinical criteria for severe disease will be counted in the numerator. All children recruited will be in the denominator.

Severe disease will be defined in a separate document.

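### Counting children without a valid SpO2 reading as normoxaemic, over all recruited, makes reported hypoxaemia prevalence depend on oximeter coverage, and the complication table has no measured row at 94% or above

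*SAP*

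**What the plan says.** SAP 6.1.1 (SpO2 values) sets the rule for absent readings: "If SpO₂ value is not available, the child will be assumed normoxaemic". Values below 40% are called spurious, treated as absent, and so also become normoxaemic. Readings from 40% to below 70% are kept: "the child will be assumed (with low accuracy) to have severe hypoxaemia".

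For the prevalence outcome (SAP 6.1.5.1) and for severe hypoxaemia without other signs of severe disease (SAP 6.1.5.3), the denominator is: "All children recruited will be in the denominator". No second denominator is given for either.

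SAP 6.1.5.2 tabulates severe complications for SpO2 below 90%, 90 to below 92%, 92 to below 94%, spurious and missing: "Each SpO₂ group will be the denominator of each proportion". It has no row for measured values of 94% or more.

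Who should have been measured differs by country. SAP 4.2 says: "While in Kenya pulse oximeter was indicated for all children, in Senegal, pulse oximeter was indicated for all young infants", and in Senegal also for older children with cough or difficulty breathing, or with a red or yellow IMCI classification.

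Protocol section 4 makes both the prevalence of hypoxaemia by severity and its association with adverse outcomes a named objective.

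**The concern.** The planned prevalence mixes two quantities: how common hypoxaemia is, and how often a valid reading was recorded. It will move with oximeter uptake. It will also differ between Kenya and Senegal because the indication differed, even if the burden were the same.

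Protocol 6.3 gives a reason to think unmeasured children are normoxaemic: hypoxaemia is considered very unlikely in mild disease. That reason does not cover everyone who lacks a reading. It does not cover young infants, whom the same section describes as having relatively high prevalence. Nor does it cover older children with cough or difficulty breathing, or a red or yellow classification, who were not measured. It does not cover children whose value was discarded as spurious. It may still fit mildly ill older children in Kenya, although oximetry was recommended for them too.

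For the association objective, the complication table shows risk in the hypoxaemic bands with no measured non-hypoxaemic group next to them.

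**Working it through.** The documents state no hypoxaemia prevalence and no SpO2 coverage, so there is no figure of the plan's to reproduce. The check is an identity plus an illustration.

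**Identity.** Let c be the share of recruited children with a valid reading. Then planned prevalence = c × prevalence among measured children. This follows directly from SAP 6.1.1 and 6.1.5.1. The measured-only figure is 1/c times the planned one: 1/0.9 = 1.11, 1/0.7 = 1.43, 1/0.55 = 1.82.

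**Between countries.** Suppose prevalence among measured children were 2% in both countries, with coverage of 90% in one and 55% in the other (all assumed). The planned figures would be 0.9 × 2% = 1.8% and 0.55 × 2% = 1.1%, a gap due to coverage alone.

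**Against the truth.** Let p be true prevalence among all recruited, and r the prevalence in children without a valid reading divided by that in measured children. Accepted readings are taken as correct.

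- Measured-only = p / (c + (1 − c) r)
- Planned = c p / (c + (1 − c) r)

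For example, with p = 2%, c = 0.7 and r = 0.5, the divisor is 0.7 + 0.3 × 0.5 = 0.85. Measured-only is 2% / 0.85 = 2.35% and planned is 0.7 × 2.35% = 1.65%.

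Results for p = 2% (assumed), shown as planned / measured-only:

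| Coverage c | r = 0 | r = 0.5 | r = 1 | r = 2 |
|---|---|---|---|---|
| 0.9 | 2.00% / 2.22% | 1.89% / 2.11% | 1.80% / 2.00% | 1.64% / 1.82% |
| 0.7 | 2.00% / 2.86% | 1.65% / 2.35% | 1.40% / 2.00% | 1.08% / 1.54% |
| 0.5 | 2.00% / 4.00% | 1.33% / 2.67% | 1.00% / 2.00% | 0.67% / 1.33% |

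**Which figure is closer.** With D = c + (1 − c) r, the planned figure falls short of p by p(1 − c) r / D, and the measured-only figure exceeds p by p(1 − c)(1 − r) / D. These are equal at r = 0.5 whatever the coverage (at c = 0.7, 0.35 percentage points each way). Below r = 0.5 the planned figure is closer, and above it the measured-only figure is closer. For r between 0 and 1 the two bracket the truth. For r above 1 both are too low.

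**Errors in the other direction.** The planned figure is a lower bound only with respect to absent and spurious readings. Retained readings of 40 to below 70% could push it up. So could altitude, for which SAP 6.1.5.1 says: "Only few facilities from one district in Kenya were above 2000m but cut-off for referral was not adjusted", and applies no adjustment.

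**Complication table.** The bands in 6.1.5.2 plus spurious and missing leave out only measured values of 94% or more. Subtracting the listed groups from the post-intervention total in SAP 6.1.2.1 gives that group as one combined row. It cannot separate 94 to below 95% from 95% and above. That split matters because SAP 6.1.1 classes 92 to below 95% as moderate hypoxaemia in Senegal but not in Kenya.

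**The case against.** The strongest reply is that much of this can be recovered. SAP 6.1.1 already plans an SpO2 distribution with missing and spurious rows, so overall measured-only prevalence is one division away. In Kenya, and among young infants, every child was indicated, so the valid-reading and indicated-child figures coincide. The combined row at 94% or above follows by subtraction, and 6.1.5.2 delivers the outcome as Protocol 6.4.1 words it. The all-recruited denominator also matches the target population in Protocol section 4, and it is the better figure when r is below 0.5, as the protocol expects for mildly ill children.

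These points stand as limits on weight. They do not remove the problem. A figure that readers must rebuild is not a planned output, and prevalence among indicated older children in Senegal with a valid reading cannot be rebuilt at all. Adherence in SAP 4.2 counts any SpO2 recording, readable or not, so it is not valid-reading coverage. SAP 6.3 will describe missing data by indicators such as referral and severe disease, but no sensitivity analysis there or in 6.2.4 addresses missing SpO2. The descriptive hypoxaemia analysis of routine data in Protocol 7.3.2 covers facilities outside the pre-post study. The exploratory work on alternative cut-offs is deferred by SAP 3.1.4 to another document.

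On altitude, Protocol 6.3 considers an effect on cut-offs below 2500 m unlikely, but Protocol 6.1.1 gives one county's range as reaching 2700 m. The upward effect is therefore possible but not established.

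A valid-reading denominator has its own faults. Measured children in Senegal are a selected group, and any false low readings are magnified by 1/c. That is a reason to show both figures rather than to replace one with the other.

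**Conclusion.** The concern holds. As planned, the proportions in SAP 6.1.5.1 and 6.1.5.3 are valid-reading coverage times the proportion among measured children, and they are presented as if they described all recruited children. In the illustration with 2% true prevalence and 70% coverage, the planned figure lies between 2.0% (r = 0) and 1.08% (r = 2). The real size is unknown because coverage, prevalence and r are not in the documents, and the calculation takes accepted readings as correct. The complication table omits the measured comparison group that the association objective needs, although one combined row can be obtained by subtraction. These are descriptive, post-intervention outcomes of interest. The primary outcomes and the sample size are not affected. The change should be made because it serves a named objective and is cheap.

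**What to change.** In SAP 6.1.5.1 and 6.1.5.3, keep the all-recruited proportion and label it as assuming that no child without a valid reading was hypoxaemic. Beside it report, by country and age group:

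- (a) the proportion among all children with a valid reading;
- (b) the proportion among indicated children with a valid reading;
- the valid-reading coverage that belongs to each.

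Use one valid-reading rule in both countries, namely the SAP's own limit of a recorded value of 40% or more. For (b), take the caregiver-reported, pre-consultation indication in SAP 4.2 as the main definition. The alternative, based "or on diagnosis made by the healthcare provider during the consultation", may itself depend on the SpO2 result and can be shown as a check. State that (a) and (b) coincide in Kenya and that measured children in Senegal are a selected group.

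In SAP 6.1.5.2, keep the spurious and missing rows and add measured rows for 94 to below 95% and for 95% and above, with risks and 95% confidence intervals. The top row should include 100%, since the top band in 6.1.1 stops below it. If risk ratios are given, use 95% and above as the common reference in both countries and present them as exploratory where numbers permit.

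The cost is SAP wording and additional table rows and columns, with no new data collection. It depends on the indication definitions that SAP 4.2 places in a separate document. SAP 6.1.2.2 and 6.1.5.4 already report a second denominator, so the format is not new to the plan.
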